4.17 Safety Analysis

Safety analysis will be performed on the All Treated Subjects analysis set using observed cases only.

4.17.1 Visual Acuity

The proportion of eyes with a ≥ 5 letters, a ≥ 10 letters and a ≥ 15 letters decrease from baseline (i.e. change from baseline ≤ -5 , -10 and -15 letters, respectively) will be summarised by visit, by eye, by period as well as overall in the same categorical summary tables mentioned in [Section 4.16.1](#). The corresponding 95% CI will be presented (See [Section 4.2](#)).

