1997, Cheng, Azen et al. 2001, Anderson, Fineman et al. 2006, Stein, Zacks et al. 2009, Recchia, Scott et al. 2010). Post-operative intraocular inflammation caused by vitrectomy is often associated with transient or sometimes permanent visual impairment. Another complication of vitrectomy is cataract formation, which may require an additional surgical procedure (cataract extraction) (Park, Marcus et al. 1995, Cheng, Azen et al. 2001, Recchia, Scott et al. 2010). In addition, the surgical procedure is performed under general anesthesia, which includes the risks of dizziness, confusion, nausea and vomiting.

Loss of VA has been observed post-treatment with AAV2-REP1. This VA loss was determined by the Investigators to be plausibly related to the administration of AAV2-REP1, however without definitively attributing the cause to either the study procedure or the GTMP. Complications from the surgical procedure are expected and are not considered reportable as suspected unexpected serious adverse reactions (SUSARs) unless also assessed to be at least possibly related to AAV2-REP1. The Reference Safety Information described in the current version of the Investigator's Brochure for AAV2-REP1 defines *visual acuity reduced* as an expected serious adverse drug reaction, with a frequency of 4/79 (5.1%), defined as common ($\geq 1/100$ to $<1/10$). Loss of VA is considered an identified risk of AAV2-REP1. Inflammation is a potential risk of AAV2-REP1.

See the Investigator's Brochure for further details.

Thus, although there are risks associated with the administration of the study treatment via vitrectomy and retinal detachment, the potential for benefit in the form of improved VA that may be provided to subjects with CHM following treatment with AAV2-REP1 provides an acceptable risk-benefit profile for participation in this study.

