10.10 Unscheduled Visits

If clinically indicated, subjects may need to return to the site for an unscheduled visit. At a minimum, the following assessments will be performed (ophthalmic assessments will be conducted on any eye deemed appropriate by the Investigator):

- BCVA
- Full ophthalmic examination, including IOP, a slit-lamp examination, lens opacity, and dilated fundus examination
- SD-OCT
- AE/SAE monitoring
- Concomitant medication, procedures and treatment review (including review / return of the corticosteroid diary card, if applicable)

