4.2 Conventions

Summary statistics will be presented for continuous variables, by way of number of subjects, mean, standard deviation (SD), median, first and third quartiles (Q1 and Q3, respectively), 5th and 95th percentiles (P05 and P95, respectively), minimum and maximum. For categorical variables including binary variables, counts and percentages will be presented. Percentages will be calculated using the total number of eyes in the respective column or the total number of eyes with an assessment, the total number of treated subjects, depending on the nature of the analysis.

In addition, 95% 2-sided confidence intervals (CIs) will be presented, where specified. The 95% CI of the mean value of an assessment will be calculated using the t-test formula. The 95% CI of the mean of change from baseline of an assessment will be calculated using the t-test formula. In case of percentages, the CI will be computed using the Clopper-Pearson method. (See [Section 4.21](#) for the corresponding SAS code).

No formal statistical comparison will be performed.

Summary statistics will be presented by period and overall for all endpoints. For selected endpoints (see details below), summary statistics will also be presented by Surgery Window (Short [<6 months], Medium [6-12 months] and Long [>12 months]) and overall. Where appropriate, summary statistics will be displayed by eye (SE1 and SE2), and by period.

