4.16.1 Visual Acuity

Best-corrected visual acuity (BCVA) and change from baseline will be summarised by visit, by eye, by period as well as overall. The corresponding 95% CIs will be calculated (See [Section 4.2](#)).

Furthermore, the proportion of eyes with a ≥ 10 letters increase, a ≥ 15 letters increase, and an increase or a loss < 5 letters (i.e. change from baseline > -5 letters) will be summarised by visit, by eye, by period as well as overall. The corresponding 95% CI will be presented (See [Section 4.2](#)).

The above main analyses will use the observed case method only. Imputation using LOCF method regardless of the reasons of missing data will be performed for supportive analyses (See [Section 4.8](#)).

In addition to the by-period, by-eye presentation mentioned above, as supportive analyses, for both continuous and categorical endpoints, the period 2 Study Eye 1 data will be presented by

remapping them to visits after their last visit in period 1 and calculating change from baseline using baseline at period 1 for the same eye (Study Eye 1). This way a full picture of Study Eye 1 treatment journey during the entire study will be presented.

For all assessments of periods 1 and 2 of Study Eye 1, the data records will be assigned to calculated visit window (using study day) as described in [Table 2](#) below. The window of the visits following baseline (including unscheduled visits) will be constructed in such a way that the upper limit of the interval falls half way between the two visits.

If a patient has more than one assessment included within a window, the assessment closest to the target day will be used. In case of ties between observations located on different sides of the target date, the value with the later date will be used.

Table 2 **Visit Assignment Windows**

Day / Month	Target Day	Day Range included in the visit
Baseline	0	The last assessment on or before day 0
Day 1	1	Day 1
Day 3	3	Day 2 to 5
Day 7	7	Day 6 to 10
Day 14	14	Day 11 to 22
Month 1	30	Day 23 to 61
Month 3	91	Day 62 to 136
Month 6	182	Day 137 to 272
Month 9	273	Day 228 to 318
Month 12	365	Day 319 to 410
Month 15	456	Day 411 to 501
Month 18	548	Day 502 to 593
Month 21	639	Day 594 to 684
Month 24	731	Day 685 onwards

Both continuous and categorical endpoints for BCVA will be summarised by subgroups mentioned in [Section 4.7](#).

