4.20 Changes in Planned Analyses from the Protocol

There are some changes to the planned analyses described in the protocol.

1. The protocol refers to the assessment of Fixation Location. Because of a change in the way microperimetry data are collected, fixation location is not available in the database. Therefore, Fixation Location was removed from the SAP.
2. The protocol mentions that specific analyses of the sensitivity points (microperimetry) will be performed. These analyses are not included in the SAP as they are considered as exploratory across the BIIB111 program and will be performed as post-hoc analyses, if needed to be consistent with other studies in the same program.
3. For consistency of other studies in the program, time to resolution of AEs will not be summarized.
3. The protocol specifies that LOCF will be used as imputation method for efficacy analyses. The main analyses of categorical and continuous efficacy endpoints will use the observed case method, as the main purpose of the study is the evaluation of BCVA from a safety perspective. Additional supportive analyses of BCVA-related endpoints, including LOCF imputation, will be applied and are described in detail in [Section 4.16.1](#).

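### Measured BCVA loss is tabulated only visit by visit; no any-time or last-assessment loss proportion per eye is specified, and no rule places unscheduled or early-termination BCVA in the main tables

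*SAP*

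**What the plan says.** SAP 4.17.1 defines three loss categories (at least 5, 10 and 15 letters) and says that the proportions of eyes in each "will be summarised by visit, by eye, by period as well as overall in the same categorical summary tables mentioned in" SAP 4.16.1. SAP 4.17 adds: "Safety analysis will be performed on the All Treated Subjects analysis set using observed cases only". The word overall is a display margin. SAP 4.2 puts it as "Summary statistics will be presented by period and overall for all endpoints", and nothing there makes it a worst or any-time value.

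On visit assignment, the only rule is in SAP 4.16.1, in the text on the supportive remapping of Study Eye 1 (SE1): "For all assessments of periods 1 and 2 of Study Eye 1, the data records will be assigned to calculated visit window". Those windows take in unscheduled visits. When several values fall in one window, the value nearest the target day is kept, not the worst. No matching rule is given for Study Eye 2 (SE2).

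BCVA is measured at the visits in question. Protocol 10.10 says "If clinically indicated, subjects may need to return to the site for an unscheduled visit" and lists BCVA in the minimum set. Protocol 10.9 lists it for the early-termination (ET) visit.

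SAP 4.3 gives SE1 a new baseline at the start of Period 2, and Period 1 ends the day before second-eye surgery. SAP 4.20 explains the choice of observed cases "as the main purpose of the study is the evaluation of BCVA from a safety perspective".

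**The concern.** In a single-arm safety study, a reader will want to know what fraction of treated eyes lost 15 letters or more, both at their last measurement and at any point after the post-operative recovery period. No table specified from measured BCVA is designed to answer that. Each by-visit column has its own denominator (eyes seen at that visit), so an eye that lost vision and left is absent from later columns. A loss that appears and recovers between scheduled visits may not be seen at all.

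The main tables serve SE1 least well. After second-eye surgery its change is counted from the new Period 2 baseline, so a loss already present at that point no longer shows. Its whole course from its own surgery appears only in the supportive remapping.

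Loss of acuity is the identified risk (Protocol 5.4), so its summary should not depend on visit attendance or on an unstated assignment rule.

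**Working it through.** **Inputs.** Planned size is 60 subjects and 120 treated eyes (SAP 3.6): 60 × 2 = 120, which reproduces. SAP 4.3 names 6 subjects whose first eye was treated in an antecedent study. If they are among the 60, this study treats 120 − 6 = 114 eyes: 60 second eyes and 54 first eyes. For intervals, SAP 4.2 says: "In case of percentages, the CI will be computed using the Clopper-Pearson method". The documents give no dropout rate and no persistence of loss, so both are assumed below. All examples assume that 60 second eyes are treated.

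**Formulas.** For x eyes of n, the lower limit is the 2.5% point of Beta(x, n − x + 1) and the upper limit is the 97.5% point of Beta(x + 1, n − x). For x = 0 the upper limit is 1 − 0.025^(1/n).

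**Illustration 1: affected eyes leave.** Suppose 3 of 60 second eyes lose at least 15 letters and leave through the ET visit before Month 12, and the other 57 attend without such a loss.
- Month 12 column: 0/57, upper limit 1 − 0.025^(1/57) = 6.3%.
- Per-eye proportion: 3/60 = 5.0% (95% CI 1.0% to 13.9%).
- If ET were shown as its own row with ET attenders as denominator, it would read 3/3. The figure 3/60 would still not appear.

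**Illustration 2: the same columns fit different rates.** Suppose each of the four visits from Month 1 to Month 12 shows 3/60.
- Same three eyes each time: any-time proportion 3/60 = 5.0% (1.0% to 13.9%).
- Different eyes each time: 4 × 3 = 12, so 12/60 = 20.0% (10.8% to 32.3%).

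**Illustration 3: losses seen only at unscheduled or ET visits.** One to three such eyes added to 3/60 give 4/60 = 6.7% (1.8% to 16.2%) up to 6/60 = 10.0% (3.8% to 20.5%).

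**Side check on the one existing rule.** In SAP Table 2, Month 6 covers Days 137 to 272 and Month 9 covers Days 228 to 318. They overlap by 272 − 228 + 1 = 45 days. The half-way rule gives (182 + 273)/2 = 227.5, so Month 6 should end at Day 227. As written, an SE1 value from Day 228 to Day 272 has no unique visit.

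**The case against.** Three stronger readings are tempting, and the documents support none of them.

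First, a reader might infer that unscheduled and ET values are left out of the main tables. The SAP is silent; it does not exclude them. ET is a named column of the visit schedule with BCVA marked, and a by-visit table could show it.

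Second, a reader might infer that no per-eye loss figure exists. SAP 4.17.11.4 plans the percentage of eyes with a loss of at least 15 letters at Month 12, split by immunogenicity status. SAP 4.17.10 plans Visual Acuity Reduced TEAEs by eye, by period or surgery window, and by time to onset. Protocol 11.1.1.2 makes specified measured losses of at least 15 letters reportable as SAEs, so these tables are not purely a matter of judgement.

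Third, a reader might set the missing rate against the 4/79 in Protocol 5.4. That figure is the frequency of a serious adverse drug reaction. Its nearest counterparts are the planned serious TEAE tables, so it is no benchmark for measured letter loss.

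The best counter-argument is LOCF. SAP 4.8 and 4.16.1 plan it as support for BCVA categorical endpoints, and the loss rows sit in the same tables. A Month 12 LOCF column would come close to a last-assessment proportion, and in Illustration 1 it would return 3/60 if ET values feed it. For the 5-letter category, the complement of the SAP 4.16.1 category of change above −5 letters already gives this. For 10 and 15 letters it is unclear, because SAP 4.17 says observed cases only. Nor does the SAP say that ET or unscheduled values feed the LOCF.

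Some of the objection stands. Illustration 1 makes every leaver an affected eye, and such losses might show in earlier columns. An any-time figure also rises with the number of measurements through test variability, more so at 10 letters. But the cover remains partial. TEAEs exclude worsening judged consistent with natural progression (Protocol 11.1.1.1). The Month 12 split is confined to subjects with evaluable immunogenicity samples and omits eyes that left earlier.

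**Conclusion.** The gap is real but limited. From measured BCVA, the SAP specifies no any-time or last-assessment per-eye proportion for losses of 10 or 15 letters in its main tables, and it states no rule that brings unscheduled or ET values into them. By-visit prevalence does not fix the per-eye rate: 3/60 at each of four visits is compatible with anything from 5.0% to 20.0% of eyes. It can also understate the rate when affected eyes leave, as in 0/57 against 3/60. These sizes rest on assumed dropout and persistence and are not forecasts.

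A reader might take this as a serious error in the safety analysis. The documents do not support that: the study is descriptive, the data are collected, and other planned tables capture part of the same risk. It is a cheap improvement.

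**What to change.** Add one table to SAP 4.17.1. Per eye, and from the baseline before that eye's own surgery, give the number and percentage with a loss of at least 15 letters, and of at least 10 letters:
- (a) at the last available assessment, including ET and unscheduled visits at any time;
- (b) at any assessment from Month 1 on, including those visits.

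Use Clopper-Pearson intervals. Show SE1 and SE2 treated in this study separately, and SE2 also by surgery window. Starting (b) at Month 1 keeps the expected early surgical dip out of it, while (a) still catches eyes that leave before Month 1.

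In the text, state how unscheduled and ET values are assigned to visits for both eyes, remove the Table 2 overlap, and say whether LOCF applies to the loss categories and which values feed it.

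The cost is one more table from data already collected, by a method already in the SAP. The reported loss rate may look less favourable. Because (b) rises somewhat with test variability, it should be shown beside (a).

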4.7 Subgroup Analysis

Demographic and baseline characteristics will be summarised by Surgery Site. The efficacy endpoints of BCVA will be summarised by the subgroups defined in [Table 1](#).

Table 1 Subgroups Defined at Baseline

	Values
Age 1	≤ 50 years old > 50 years old
Age 2	≤ 60 years old > 60 years old
Age 3	\leq median age $>$ median age
Race	White Non-white (American Indian or Alaska Native, Asian, Black or African American, Native Hawaiian or Other Pacific Islander)
Region	America Europe
Surgery Site	Each of the surgery sites
Surgery Window	Short [< 6 months], Medium [$6-12$ months] Long [>12 months] Overall

In addition, TEAE will also be summarized by Surgery Window (Short [< 6 months], Medium [$6-12$ months] and Long [>12 months]) and all surgery windows combined.

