4.16.4 Macular Integrity Assessment Microperimetry

Mean Sensitivity, Bivariate Contour Ellipse Area 63%, Bivariate Contour Ellipse Area 95% and Fixation Losses will also be summarised by visit, by eye, by period as well as overall. The corresponding 95% CIs will be calculated (See [Section 4.2](#)).

The number and percentage of subjects within each category of Fixation Stability will be summarised by visit, by eye, by period and by surgery window as well as all surgery windows combined. Shift from baseline will also be evaluated.

The categories for the shift from baseline for ‘Fixation Stability’ assessment are defined as follows:

- Stable at Baseline to Stable
- Stable at Baseline to Relatively Unstable/Unstable
- Relatively Unstable/Unstable at Baseline to Stable
- Relatively Unstable/Unstable at Baseline to Relatively Unstable/Unstable

Where microperimetry data are collected using the automated text files, the following algorithm will be used to define the value of Fixation Stability.

- If $P1 \geq 75\%$, then fixation stability is considered as stable.
- If $P1 < 75\%$ and $P2 \geq 75\%$, then fixation stability is considered as relatively unstable.
- If $P1 < 75\%$ and $P2 < 75\%$, then fixation stability is considered as unstable

Image quality will be listed only. This includes image completeness, focus/clarity and field definition.

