4.17.2 Intraocular Pressure

Intraocular pressure and change from baseline will be summarised by visit, by eye, by period as well as overall.

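### The SAP never defines *overall* for BCVA change and letter loss; if it means the two periods stacked within an eye, the row is not a post-treatment vision-loss rate

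*SAP*

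**What the plan says.** Four places in the SAP bear on the meaning of *overall*.

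- SAP 4.2 sets the general rule: "Summary statistics will be presented by period and overall for all endpoints". The next sentence limits window summaries: "For selected endpoints (see details below), summary statistics will also be presented by Surgery Window". That sentence also ends with the word *overall*, this time beside the windows.
- SAP 4.16.1, on efficacy: "Best-corrected visual acuity (BCVA) and change from baseline will be summarised by visit, by eye, by period as well as overall". SAP 4.17.1 puts the proportions losing at least 5, 10 and 15 letters in the same categorical tables, "summarised by visit, by eye, by period as well as overall in the same categorical summary tables".
- SAP 4.17.2 uses the same form for a measure with no window summary: "Intraocular pressure and change from baseline will be summarised by visit, by eye, by period as well as overall".
- SAP 4.7, Table 1, ends its surgery-window entry with "Long [>12 months] Overall". SAP 4.16.4 spells that meaning out for fixation stability: "by visit, by eye, by period and by surgery window as well as all surgery windows combined".

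SAP 3.3 has both eyes examined in both periods. Under SAP 4.3, Period 1 ends the day before SE2 surgery, and each eye takes a new baseline for each period. SAP 4.2 fixes the interval for proportions: "In case of percentages, the CI will be computed using the Clopper-Pearson method".

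**The concern.** If *overall* means both periods together within an eye, the row mixes different quantities.

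- **SE2:** throughout Period 1 this eye is untreated. Its Period 1 records would sit beside its records after surgery.
- **SE1:** its Period 2 records are timed from the fellow eye's surgery and compared with a value taken after SE1's own treatment. Suppose an eye loses 15 letters after its own surgery and then stays level. It counts as a 15-letter loss in Period 1 and as no change in Period 2.

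Safety is the study's only objective, and protocol 5.4 lists loss of visual acuity as an identified risk. A row labelled *overall*, with a 95% interval, could easily be quoted as the vision-loss rate after treatment. The SAP gives the programmer no rule for choosing between the two meanings.

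**Working it through.** The documents state no share of records, so there is no figure of theirs to reproduce.

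**Inputs**
- About 60 subjects (SAP 3.6; protocol 13.1).
- 6 subjects whose first eye was treated in an antecedent study, contributing to Period 2 only (SAP 4.3, 4.4).
- Both eyes assessed in both periods (SAP 3.3).
- About 20 subjects in the long window (SAP 3.1).
- Assumed: the 6 are among the 60, every second eye is treated, early visits are all attended, and records are stacked.

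**Early visits, per eye**
- Period 1 records: 60 − 6 = 54. Period 2 records: 60. Total: 114.
- SE2 records before SE2 surgery: 54/114 = 47.4%.
- SE1 records measured from the value before the fellow eye's surgery: 60/114 = 52.6%. Of these, 54 (54/114 = 47.4%) are re-baselined within GEMINI. The other 6 (6/114 = 5.3%) are antecedent eyes that have only a Period 2 baseline.

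**Sensitivity of the SE2 share**
- The 6 are additional to the 60: 60/126 = 47.6% (SE1: 66/126 = 52.4%).
- 50 to 70 subjects: 44/94 = 46.8% to 64/134 = 47.8%.
- 3, 5 or 10 second eyes never treated: 54/111 = 48.6%, 54/109 = 49.5%, 54/104 = 51.9%.

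**Month 12**, taking Period 1 records from a long window of 20 that holds all or none of the 6:
- SE2 before surgery: 14/74 = 18.9% to 20/80 = 25.0%.
- SE1 on the Period 2 baseline: 60/74 = 81.1% to 60/80 = 75.0%.

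**Direction of error.** Let p be the loss rate in SE2 records after surgery and q the rate in those before it. The early SE2 row shows (60p + 54q)/114. Take 3 losses in 60, p = 5.0%, purely as an illustration:
- q = 0: 3/114 = 2.6%.
- q = 5.0%: 5.0%.
- q = 8%: (3 + 4.32)/114 = 6.4%.

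At q = 0 the Clopper-Pearson interval moves from 1.0%–13.9% (3/60) to 0.5%–7.5% (3/114). The stacked n of 114 comes from only 60 eyes, 54 of them counted twice, while the formula treats all 114 as independent.

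**Table 2, a separate slip.** SAP 4.16.1 puts each upper limit half-way to the next visit. For Month 6 (target Day 182) and Month 9 (Day 273) that is (182 + 273)/2 = 227.5, so Month 6 should end at Day 227. It is printed as Day 137 to 272, and Month 9 as Day 228 to 318. Days 228 to 272 therefore belong to both windows. The closest-assessment rule chooses among records within one window. It does not say which window a single record belongs to. Remapped SE1 records can fall there: with SE2 surgery on, say, Day 150, the Period 2 Month 3 visit lands on SE1 Day 150 + 91 = 241.

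**The case against.** The strongest reply is that the harmless reading has support specific to BCVA. SAP 4.16.1 and 4.7 summarise BCVA by the Table 1 subgroups, and Table 1 places *overall* under surgery window. SAP 4.3 ties each change to the baseline of the same period and the same eye. This stands as a real alternative, so it cannot be said that the SAP definitely plans the mixed row. It does not settle the matter. IOP carries the same wording with no window summary, and SAP 4.2 applies *overall* beside period to every endpoint.

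Second, the SAP's unit is eyes, not records. SAP 4.2 takes percentages over eyes in the column or eyes assessed, so 114 exceeds the roughly 60 SE2 eyes. This also stands: the 47% and 53% need stacking, which the SAP does not state. But if each eye counts once per visit, no rule says whether its Period 1 or Period 2 record is used. Keeping Period 1 records wherever they exist would leave 54/60 (90%) of the early SE2 row untreated. Keeping Period 2 records would leave none.

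Third, interpretable results are already planned: the SE1-Period 1 and SE2-Period 2 cells, and a supportive SE1 analysis across both periods from the Period 1 baseline. The study is descriptive, and no decision rule in the documents uses the *overall* row. All of this stands and keeps the point minor.

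A reader might also infer that the intervals would be badly too narrow. The documents give no within-eye correlation between periods. At a common 5% rate, Clopper-Pearson coverage is 94.1% at an assumed correlation of 0.3 and 92.1% at 0.5, and neither value has a source.

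**Conclusion.** The term is undefined, and the reading best supported by SAP 4.2 gives a row that should not be read as a vision-loss rate after treatment. The size is about half of early records and about 19% to 25% of SE2 records at Month 12, under the stacking, enrolment, attendance and window assumptions listed above.

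Three stronger conclusions might be drawn, and the documents support none of them.
- That the row must understate vision loss: the direction depends on loss in the added records.
- That the trial has no valid loss rates: the own-surgery cells and the SE1 remapping do not depend on what *overall* means.
- That a new pooled treated-eye rate is needed: this is optional, and separate eye results already describe first and second administration.

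The Table 2 overlap is a plain error whichever meaning is intended, but it touches only the supportive SE1 display. Severity is minor for both.

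**What to change.** In SAP 4.2, 4.16.1 and 4.17.1, state that for ocular endpoints analysed as change or shift from baseline, *overall* means all surgery windows combined within eye and period, using the wording already in SAP 4.16.4. Add that Period 1 and Period 2 records are not pooled within an eye. Say that the same applies to the other places with this phrase: the continuous measures in 4.16.4, and 4.17.2 to 4.17.5. Adverse-event totals across periods are a different matter and need no change.

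In Table 2, change the Month 6 range to Day 137 to 227.

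The cost is a sentence or two of SAP wording and one corrected number. No extra subjects, visits or new analyses are needed. What is given up is a single periods-combined figure per eye, which has no clear meaning for these endpoints.
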